3. STATISTICAL CONSIDERATIONS

Statistical Analyses: We will compare baseline patients' demographic characteristics (age, gender, race and levels of education) between the intervention and control group using two sample t-tests for continuous variables and Chi-square tests for categorical variables to determine whether the two groups are balanced in these variables. Variables that are found to be unbalanced will be included as covariates in all models comparing outcomes between the two groups. Intention to treat approach will be used in all analyses.

a. Primary Specific Aim: Delirium/coma free days by day 7 will be compared using analysis of covariance (ANCOVA) model with group (intervention versus control) as the independent variable while adjusting for the baseline patients' demographic variables not balanced between the two groups. For patients discharged before day 7, the days from discharge to day 7 will be counted as delirium/coma free. For patients who died before day 7, 0 delirium/coma free days will be counted from date of death to day 7. We have used the same approach in our previous trials and this approach is able to appropriately handle potential missing data due to discharge or death of patients before day 7.¹⁷

Secondary Specific Aim 1: Mixed effects models will be used to compare delirium severity (CAM-ICU-7), pain (CPOT) and anxiety scores (VAS-A) measured twice daily from randomization to day 7, time of death or discharge. In each of the models, repeated CAM-ICU-7, CPOT or VAS-A scores will be the outcome variable respectively. Group, time, group and time interactions will be included as independent variables while adjusting for potential baseline covariates. Significant group and time interactions will indicate differences in changes of these outcomes between the two groups. Post-hoc analyses will be conducted to determine the earliest times when significant differences between these outcomes can be detected. We will compare various variance covariance structures including autoregressive (AR) and variance components blocked by time of the day (am versus pm) using the likelihood ratio tests to determine the most appropriate covariance structure. We will also examine potential non-linear trajectories of change in these outcomes by including quadratic time in the models and by fitting spline models.

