- **b. Secondary Specific Aim 2:** ANCOVA models will be used to compare IU-TBANS, PHQ-9, and GAD-7 collected at three months post hospital discharge with group as the independent variable while adjusting for potential baseline covariates.
- **c. Missing Data:** We expect up to 20% of patients who may not complete the primary outcome at day 7 due to death in the ICU or discharge before day 7. We will conduct sensitivity analyses with varying assumptions for the patients with missing outcomes to determine the robustness of our findings. The mixed effects model we propose for Secondary Aim 1 is robust to the missing at random assumption and is unbiased if we include all relevant covariates in the model. We will also compare baseline characteristics of patients with 3-month

assessment and those who are lost to follow-up and adjust for the variables associated with missing data to ensure unbiased estimation and inference.

d. Sex as a Biological Variable: Both male and female patients will be included in the trial. We do not anticipate treatment efficacy will differ by sex. We will include sex as a covariate in each analysis to

determine whether estimated treatment effects differ by sex.

e.Sample Size and Power: Sample size estimation is based on the observed effect size from our pilot data where the intervention group had higher delirium/coma free days from the control group with estimated effect size of 0.52. Using two sample t-test, we estimate that we will need 128 total patients with complete data to detect an effect size of 0.5SD or higher at α =0.05. For robustness of results, we also estimated power if we assume Poisson distribution for mean delirium/coma free days with a total 128 patients observed at day 7, we will have 98.7% power to detect group difference at α =0.05 using the nonparametric Wilcoxon test. Allowing up to 20% attrition rate for patients dropping out before day 7, we will enroll 160 total patients for this trial (80 per group).

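### Sex enters the models only as a covariate, which cannot show whether the treatment effect differs by sex, the purpose the plan gives for it

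*Combined protocol and SAP*

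**What the plan says.** Section 3, Statistical Considerations, item d (Sex as a Biological Variable) first states an expectation: "We do not anticipate treatment efficacy will differ by sex". It then gives the method, "We will include sex as a covariate in each analysis to", and its purpose, "determine whether estimated treatment effects differ by sex".

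The models themselves are set out under the separate aims:

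- Primary aim: "analysis of covariance (ANCOVA) model with group (intervention versus control) as the independent variable while adjusting for the baseline patients' demographic variables not balanced".
- Secondary Aim 1, the repeated measures: "Group, time, group and time interactions will be included as independent variables while adjusting for potential baseline covariates".
- Secondary Aim 2, the three-month outcomes: ANCOVA "with group as the independent variable while adjusting for potential baseline covariates".

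The opening paragraph of the same section lists gender among the baseline variables tested for balance and then says: "Variables that are found to be unbalanced will be included as covariates in all models comparing outcomes between the two groups".

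**The concern.** The method in item d does not fit its purpose. Entering sex as a covariate adjusts for a difference in average outcome between men and women. Whether the treatment works differently in men and women is another question, and it needs a term that lets the treatment effect vary by sex. No model in the plan has one.

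If the plan is followed as written, two misreadings are open. The report could say that sex differences in efficacy were examined, when the model had assumed there were none. Or the sex coefficient could be read as evidence on effect modification, which it is not.

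A smaller point concerns the main models. Item d puts sex in every analysis, while the opening paragraph and the primary-aim sentence bring in demographic variables through a balance test. If gender turns out balanced, a reader of the primary-aim sentence alone would leave sex out, and a reader of item d would put it in.

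**Working it through.** **What each model can show.** Code group as 0/1 and sex as 0/1.

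- Covariate model: mean = b0 + b1·group + b2·sex. The treatment effect is b1 in the first sex and (b0 + b1 + b2) − (b0 + b2) = b1 in the second. The two are equal by construction, and b2 compares outcome levels only.
- Interaction model: mean = b0 + b1·group + b2·sex + b3·group·sex. The effects are b1 and b1 + b3, so b3 is the difference the plan says it wants.

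**Does the plan name such a term elsewhere?** The only interaction it names is group by time: in Secondary Aim 1, in the power text for the repeated measures, and in the model for Exploratory Aim 1. The primary and Secondary Aim 2 ANCOVAs have group plus adjustment covariates.

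**Simulation of the two models.** 4,000 trials per scenario, 128 patients, equal sex split, normal outcome with SD 1, 5% two-sided tests.

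| Truth | Sex coefficient significant (covariate model) | Interaction significant (interaction model) |
|---|---|---|
| Effect 1.0 SD in one sex and 0 in the other; equal mean outcome by sex | 4% | 80% |
| Same effect in both sexes; mean outcome differs by 0.5 SD | 79% | 5% |

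Read as evidence on effect modification, the sex coefficient would miss a large real difference and would flag one that does not exist.

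**The plan's own sample size.** Inputs from item e: effect 0.5 SD, α = 0.05 (taken as two-sided), 128 with complete data, 20% attrition. The primary calculation states no power; 80% is stated for the three-month outcomes with the same effect size and test. A two-sample t-test then needs 64 per arm, 128 in total (power 80.1%), and 128 / (1 − 0.20) = 160. The plan's figures reproduce.

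**Precision once the interaction is added.** Allocation is 1:1. Let f be the proportion of one sex; the documents give no figure, so a range is shown. That sex has Nf/2 patients per arm, so its treatment effect has variance 2/(Nf/2) = 4/(Nf) in SD² units. Likewise it is 4/(N(1−f)) for the other sex. Hence

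SE of the difference in effects = √[4/(Nf) + 4/(N(1−f))].

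At f = 0.5:

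- N = 128: √(4/64 + 4/64) = √0.125 = 0.354.
- N = 160: √(4/80 + 4/80) = √0.100 = 0.316.

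The 95% half-width is 1.96 × SE. The difference detectable with 80% power is (1.96 + 0.84) × SE. Power for a 0.5 SD difference uses the noncentral t with N − 4 degrees of freedom.

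| N | Sex split | SE (SD) | 95% half-width (SD) | Detectable at 80% (SD) | Power for 0.5 SD |
|---|---|---|---|---|---|
| 128 | 50:50 | 0.354 | 0.69 | 0.99 | 29% |
| 128 | 60:40 | 0.361 | 0.71 | 1.01 | 28% |
| 128 | 70:30 | 0.386 | 0.76 | 1.08 | 25% |
| 160 | 50:50 | 0.316 | 0.62 | 0.89 | 35% |
| 160 | 60:40 | 0.323 | 0.63 | 0.90 | 34% |
| 160 | 70:30 | 0.345 | 0.68 | 0.97 | 30% |

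For 80% power at a 0.5 SD difference, the trial would need about 503, 524 or 599 patients at the three splits.

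**The case against.** The best defence is that the purpose clause fixes the aim, so a competent analyst would add the interaction, and that "We will include sex as a covariate in each analysis to" is loose wording that does not exclude one. That is possible. But the plan names interactions where it wants them and names none with sex, so a main effect is the natural reading. Even on the generous reading the term is unspecified.

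Several other points stand:

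- Sex is in no aim or hypothesis, no difference is expected, and adjusting for sex does no harm. The primary comparison, its type I error and the sample size are untouched.
- The repaired analysis reaches 80% power only for a difference of about 1.0 SD, twice the main effect the trial is sized for. It will rarely settle the question. That is a reason to report an interval, not to leave the term out.
- The balance rule does not say that only unbalanced variables may enter, so it can be followed together with item d. That point is one of clarity, not a flat contradiction.
- The precision figures apply to outcomes measured once. They do not carry over to a three-way term in the repeated-measures models, and fewer than 128 patients may supply three-month data.

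**Conclusion.** The concern holds. As specified, the models give no information on whether the treatment effect differs by sex, although the plan says they are there to determine it. This follows from the form of the model and does not depend on any assumed number.

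The size of what the repair can deliver does rest on assumptions: a single-measurement outcome, equal variances, two-sided 5% and, for the headline figures, an equal sex split. Moving to 70:30 widens the interval and lowers power by about 4 to 5 percentage points. In every case shown, a non-significant interaction would not show that the effect is the same in men and women.

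The point should be corrected before the analysis. It does not threaten the primary result.

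**What to change.** In item d, separate the two roles of sex:

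1. State that sex is a fixed covariate in every main model whatever the balance test shows, and name it in the primary-aim sentence so that the two places agree.
2. For each outcome, add one supportive model with a group-by-sex interaction. For the repeated measures, add group-by-sex-by-time with its lower-order terms.
3. Report the treatment effect in men and in women, and the interaction with its 95% confidence interval.
4. State that this is estimation with low power, and that a non-significant interaction will not be taken as evidence of equal effects.

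The cost is a sentence or two in the SAP and one extra model per outcome: seven for the primary and secondary aims (one primary, three in Secondary Aim 1, three in Secondary Aim 2), plus those for the exploratory outcomes. It needs no new data, patients or visits, and the sample size does not change.

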- **Delirium/Coma Free Days:** Delirium/coma free days will be the primary outcome for the trial. Delirium/coma free days are the number of days after randomization patients are alive free of delirium and not in coma during the seven-day study intervention phase. This outcome describes the duration of normal cognitive status where the patient is not comatose and does not have delirium and has been utilized in high impact studies. 14-17 We will utilize the Confusion Assessment Method for the ICU (CAM-ICU)75 and the Richmond Agitation Sedation Scale (RASS)⁷⁶ for assessment of delirium and coma respectively. RASS score ranges from -5 to +4 with a score of -4 or -5 (lack of response to verbal or physical stimuli) characterized as comatose and ineligible for CAM-ICU assessments. RASS scores of -3 and -2 depict moderate and light sedation, -1 drowsiness, 0 alert and calm, and +1 to +4 various degrees of agitation. Patients with a RASS score of -3 to +4 will be considered eligible for CAM-ICU assessments. The CAM-ICU score will be determined by examining the patient for (a) acute or fluctuating changes in mental status, (b) inattention, (c) altered level of consciousness and (d) disorganized thinking. Patients will be considered delirious if they display (a), (b), plus (c) and/or (d). Trained research assistants will be performing CAM-ICU twice daily after the assigned intervention. Sedation status through RASS will be collected before and after the intervention delivery. After the 7-day study intervention phase, study staff will continue to assess RASS and CAM-ICU twice daily throughout the subject's hospital stay (up till day 28).
- **2. Delirium Severity**: Delirium severity will be assessed twice daily by trained research assistants using the CAM-ICU-7 developed by [name]. CAM-ICU-7 is a seven-point scale (0-7), derived from the RASS and the CAM-ICU. The CAM-ICU-7 score ranges from 0-7; categorized as 0-2: no delirium, 3-5: mild to moderate delirium, and 6-7: severe delirium. Trained research assistants will be performing CAM-ICU-7 twice daily after the assigned intervention. After the 7-day study intervention phase, study staff will continue to assess CAM-ICU-7 twice daily throughout the subject's hospital stay (up till day 28).

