- **3. Pain:** Pain will be assessed by trained research assistants utilizing the Critical Care Pain Observation Tool (CPOT), a valid and reliable instrument in critically ill patients with and without delirium, ^{78,79} recommended by the SCCM 2018 PADIS guidelines. ²¹ CPOT uses observable physiological and behavioral indicators of pain to determine whether pain is present and can be used in nonverbal patients. It contains 4 sections, each with different behavioral categories, including facial expressions, body movements, muscle tension, and either compliance with ventilator (intubated patients) or vocalization (non-intubated patients). The score ranges from 0-2 for each section with a total score range of 0-8 with higher scores indicating more pain. Trained research assistants will be performing CPOT four times daily before and after intervention delivery. We will continue to assess CPOT twice daily after the 7-day study intervention phase throughout the ICU stay.
- **4. Anxiety:** Anxiety intensity defined as a heightened state of apprehension, agitation, and arousal, ⁸⁰ will be measured four times daily before and after assigned intervention using a 100-mm Visual Analog Scale-Anxiety (VAS-A), which measures changing anxiety and is amenable to intervention. ^{81,82} The VAS-A will be presented to all patients vertically, like a thermometer, and will be anchored on the ends by 0 = not anxious at all and 100 = most anxious ever. The VAS-A is scored using a ruler from the 0 anchor to the mark placed by the patient, which yields the current level of anxiety from 0 to 100. The same ruler will be used to score all VAS-As for consistency. [name] has used the VAS-A extensively in prior research studies, including a vertical orientation of the instrument that is sensitive and easier for critically ill patients to see, resulting in very little missing data on this important variable. ^{31,81-83} We will continue to assess VAS-A twice daily after the 7-day study intervention phase throughout the ICU stay.

Post-Hospital Discharge Outcomes:

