For Aim 2, for anxiety measured by VAS-A, we estimated power using results published by Chlan et al³¹ where the author reported (1) changes in VAS-A in both the music and control groups appear linear; and (2) the music group showed an average difference of 11 points (SD=6.48) in VAS-A scores between the two groups and the noise canceling headphones group had no-significant change over time. Assuming 128 total patients complete anxiety evaluation by day 7, a daily decrease of 0.03SD on VAS-A in the music group and no decrease in the control group, we will have 83.5% power in detecting a group and time interaction in the repeated measure model at α =0.05 assuming a first order autoregressive correlation structure with 0.4 for measurements one day apart. For pain, assuming a baseline mean of 0.54 for both groups (SD=0.63), a daily decrease of 0.2SD on CPOT in the music group and no decrease in the attention control group, we will have 80.6% power to detect a group and time interaction in a mixed effect model. We will also have 80.6% power to detect a significant interaction assuming similar trajectories for CAM-ICU-7 in the two groups. For Aim 3, we will have 80% power to detect an effect size of 0.5SD between the two groups using two sample *t*-test at α =0.05. The power estimates were conducted using the Power and GLMPower procedures in SAS 9.4.

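### The 83.5% power for VAS-A does not follow from its stated inputs (about 12-15% on a two-sided slope test), and the CPOT slope behind the 80.6% cannot hold for seven days

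*Combined protocol and SAP*

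**What the plan says.** The second paragraph of Sample Size and Power (Statistical Considerations, item e) covers the three measures of Secondary Specific Aim 1.

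- **VAS-A.** With 128 patients completing and alpha 0.05, it assumes "a daily decrease of 0.03SD on VAS-A in the music group and no decrease in the control group, we will have 83.5% power" for a group-by-time interaction, "assuming a first order autoregressive correlation structure with 0.4 for measurements one day apart". Just before this it cites a prior trial with an 11-point VAS-A difference and SD 6.48.
- **CPOT.** It claims 80.6% power for the same kind of interaction, "assuming a baseline mean of 0.54 for both groups (SD=0.63), a daily decrease of 0.2SD on CPOT in the music group" and none in the control group. Outcomes Measures, item 3, gives the instrument a "total score range of 0-8 with higher scores indicating more pain".
- **CAM-ICU-7.** It repeats 80.6% as the "power to detect a significant interaction assuming similar trajectories for CAM-ICU-7 in the two groups".

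The number of readings and the sidedness used for power are not stated. The analysis section models scores "measured twice daily from randomization to day 7, time of death or discharge", while Outcomes Measures, item 4, has VAS-A "measured four times daily before and after assigned intervention using a 100-mm Visual Analog Scale-Anxiety (VAS-A". For CPOT, neither N nor the correlation is stated. The calculations are attributed to the Power and GLMPower procedures in SAS 9.4.

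**The concern.** A slope of 0.03 SD/day separates the arms by only 0.18 SD after six days and 0.21 SD after seven. The same plan needs 128 patients to detect 0.5 SD on the primary outcome, so more than 80% power for so small a separation is not credible without a strong gain from repeated measures. The CPOT figures conflict with the scale's floor and with the VAS-A figure beside them.

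What is at stake is how Secondary Aim 1 is read. The analysis section treats the interaction as the indicator of a treatment effect. A reader who trusts 83.5% would take a null VAS-A interaction as informative. If 0.03 SD/day is really the effect expected, a null result is by far the likelier outcome even when the effect is present.

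**Working it through.** **VAS-A inputs.** From the power paragraph: 128 patients, difference in slopes d = 0.03 SD/day, AR(1) with 0.4 per day, alpha 0.05. From Enrollment and Randomization: 1:1 allocation, so 64 per arm. Assumed because unstated: two-sided test, linear time, and 7, 8, 14, 15 or 28 readings, all within day 7.

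**Formula.** With total SD 1 and V = 0.4^|ti - tj| (t in days), the standard error (SE) of the slope difference comes from the generalised least squares information matrix for both arms (separate intercepts). Power = Φ(d/SE - 1.96) + Φ(-d/SE - 1.96). For 83.5% power the required slope is (1.960 + 0.974) × SE = 2.934 × SE, and the required total N is 128 × (2.934 × SE / 0.03)².

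| Readings (days) | SE | d/SE | Power at 0.03 | Slope for 83.5% | Total N for 83.5% at 0.03 |
|---|---|---|---|---|---|
| 7 daily (0-6) | 0.0395 | 0.76 | 11.8% | 0.116 | 1,913 |
| 8 daily (0-7) | 0.0332 | 0.90 | 14.7% | 0.097 | 1,350 |
| 14 half-day (0-6.5) | 0.0358 | 0.84 | 13.4% | 0.105 | 1,567 |
| 15 half-day (0-7) | 0.0329 | 0.91 | 15.0% | 0.096 | 1,322 |
| 28 quarter-day (0-6.75) | 0.0342 | 0.88 | 14.2% | 0.100 | 1,430 |

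The stated 83.5% is not reproduced.

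**Other settings that keep 0.03 SD/day and 0.4 per day:**
- interaction F tests: 6-15%
- one-sided slope test: 19-23%
- common baseline intercept, two-sided: 23-33%
- common baseline intercept, one-sided: 34-45%

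**Check without a repeated-measures model.** A two-sided t-test with 64 per arm has 17% power for 0.18 SD and 22% for 0.21 SD.

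**Readings that come near 83.5% but depart from the text:**
- 0.03 SD per twice-daily reading (0.06 SD/day) with a common intercept: 78.7% with 14 readings, 85.8% with 15. The text says daily.
- 0.03 SD/day over 19 daily readings: 83.5%. The text stops at day 7.
- About 0.10 SD/day: 72-86% over the five schedules. The text says 0.03.

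**Consistency with the cited trial.** If 6.48 is the SD meant, 0.03 × 6.48 = 0.194 points/day, or 0.194 × 7 = 1.4 points in seven days. The cited difference is 11 points, and 11/6.48 = 1.7 SD.

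**CPOT.** The daily fall is 0.2 × 0.63 = 0.126 points. From 0.54, the music-arm mean after 0 to 6 decreases is 0.540, 0.414, 0.288, 0.162, 0.036, -0.090, -0.216. It crosses 0 at 0.54/0.126 = 4.3 days. The steepest straight line that stays at or above 0 is 0.54/6 = 0.090 points/day (0.14 SD/day) over six decreases, or 0.54/7 = 0.077 (0.12 SD/day) over seven.

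**CPOT against VAS-A.** 0.2/0.03 = 6.7, so CPOT has nearly seven times the standardised slope but lower stated power (80.6% against 83.5%). If N = 128 and AR(1) 0.4 carry over to CPOT (an assumption), the slope test at 0.2 SD/day has at least 99.9% power on all five schedules.

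**The case against.** The strongest defence is that the plan leaves sidedness, number of readings and form of test open, so a reviewer cannot claim to have rerun its calculation. The gaps are real, but varying all three while keeping the stated slope and correlation never takes power above about 45%.

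A second defence is that 83.5% may be right and 0.03 SD/day a slip in the slope or its unit. This stands as a possibility. The per-reading variant brackets the stated figure, and the mismatch with the 11-point difference points the same way. So a reader might infer that the trial really has only 12-15% power for anxiety. The documents do not support that as a flat statement: it holds only if 0.03 SD/day is the effect intended.

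On CPOT, a reader might infer that the below-zero mean proves the 80.6% wrong. It does not. Normal-theory power for an interaction depends on the slope difference in SD units, and the baseline mean does not enter. The fault is a slope that the scale cannot sustain for a week. Nor is the direction of any error known. Carrying over N = 128 and 0.4, the steepest feasible line over six decreases (0.143 SD/day) gives 95% or more on a slope test but about 53-88% on a test of all time points.

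On CAM-ICU-7, similar trajectories can fairly be read as the same standardised slope. Nothing impossible is shown there; the figure simply inherits whatever is wrong with CPOT.

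**Conclusion.** The VAS-A power is wrong as written: about 12-15% on a two-sided slope test, and at most about 45% on the most favourable variant tried that keeps the daily slope, against 83.5% stated. This rests on 64 complete patients per arm, unit total variance, AR(1) 0.4 per day, linear time and readings within day 7. Either the slope or its unit, or the power, is mis-stated, and the documents cannot settle which.

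For CPOT, the assumed slope is infeasible from the fifth daily decrease, and its 80.6% is out of line with the VAS-A figure. Its correct power cannot be computed from what is given.

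A reader might go further and infer that the trial is too small. The documents do not support that: the 128 complete and 160 enrolled come from a two-sample t-test on delirium/coma free days and do not use this paragraph. The point is a correction that should be made to the power statements for secondary outcomes.

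**What to change.** 1. Retrieve the GLMPower inputs and state them: slope and its unit, SD, number and spacing of readings, sidedness, and form of the interaction test.
2. VAS-A: if the slope or unit was mis-stated, correct it and give its source. If 0.03 SD/day is meant, restate the power that it gives (about 12-15% on a two-sided slope test). A new slope should not be chosen merely because it yields the old power.
3. CPOT: recompute with a mean trajectory that stays at or above 0, either a shallower line or a curve that flattens, and state N, correlation, number of readings and test.
4. CAM-ICU-7: update the figure carried over from CPOT and say what trajectory is assumed.

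The cost is one rewritten paragraph, with no extra patients and no change to the analysis. The only downside is a possibly less favourable stated power for VAS-A; the CPOT and CAM-ICU-7 figures could move either way.
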